4.2 Allocation implementation and concealment

The numbered opaque sealed envelopes are stored at the CRC. Envelopes containing the assignment to the treatment arm will be opened after confirming eligibility provision of informed consent at Day 0. Envelopes containing the assignment of suction blister area will be opened at visit 3.

4.3 Blinding

Due to the nature of the intervention, neither the investigators nor the participants will be blinded.

5 Methods: Data collection, management, analysis

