2.2 Objectives

The main aim of this study is to investigate in a suction blister model, whether the use of a basic skin care formulation increases the mechanical integrity/adhesion of the dermo-epidermal junction.

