3.3 Interventions

After giving informed consent and checking the in- and exclusion criteria, baseline skin measurements will be conducted (Table 3). After that one arm will be randomly selected. Subjects are instructed to apply on the selected forearm petrolatum (VASELINE, weiß Ph.Eur., Salbe). The other arm will remain untreated (control). The application of the skin care product will be twice a day in the morning and in the evening for 4, respectively 8 weeks. This should be done after washing or showering to allow the product to stay on the skin during day/ night.

Subject instructions

The subjects should inform the Investigator before using any systemic treatment which may interfere with the study assessments. Some treatments are prohibited throughout the study.

During the study, the subjects will be instructed **not to**:

- have sun exposure or UV-light sessions on the investigational areas,
- Use any topical drug or cosmetic product on the investigational areas on both arms (except usual cleaning products) which may interfere with the trial assessment (topical hyaluronan, anti-inflammatory drugs, corticoids, retinoids, α-hydroxy acids, vitamin C).
- have physical treatments on the investigational areas.

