3.4 Outcomes and variables

Because this is an exploratory study, no distinction is be made between primary and secondary outcomes.

Name	Method and metric	Time points of data collection		
Blistering Time	 Visual inspection Duration from start of suction pressure to appearance of first vesicles in minutes Duration from start of suction pressure to development of full blister in minutes (Appendix 4) 	Visit 3, Visit 5		
Skin surface Temperature	- Measurement with Skin- Thermometer ST 500 (Courage+Khazaka electronic GmbH) - Means of duplicate measurements per skin area in °C per skin area	Visit 3, Visit 5		
Stratum corneum hydratation (SCH)	- Corneometer CM 825 (Courage + Khazaka, Cologne, Germany) (Appendix 5) - Means of duplicate measurements per skin area in arbitrary units	Visit 1, Visit 2, Visit 3, Visit 4, Visit 5, Visit 6		
Epidermal and dermal hydratation	- Measurement with MoistureMeterEpiD (Delfin Technologies) (Appendix 6) - Percentage of tissue water (0- 100%) (0,5mm measurement depth)	Visit 1, Visit 2, Visit 3, Visit 4, Visit 5, Visit 6		
Epidermal thickness	- OCT (Thorlabs, Lübeck, Germany), measurements according to Trojahn et al. 2015 µm) (Appendix 8)	Visit 1, Visit 3, Visit 5, Visit 6		

Name	Method and metric	Time points of data collection
Age	Checking by looking at the ID card (metric)	Screening
Body temperature	Clinical thermometer in °C	Screening
Heart rate	Beats per minute (bpm)	Screening
Blood pressure	Millimeters of mercury (mmHg)	Screening
BMI (body height and weight)	kg/m ²	Screening
Phototype	Categories I, II, III	Screening

Both arms will be subdivided in two investigational areas, called "Area A" (upper part of the middle of the right volar forearm) respectively "Area C" (upper part of the middle of the left volar forearm) and "Area B" (lower part of the middle of the right volar forearm) respectively "Area D" (lower part of the middle of the left volar forearm) (Figure 1).

After 4 weeks (Visit 3) 2 suction blisters (Appendix 4) will be raised at the investigational Areas A or B at the right volar forearm (Figure 2). Another 2 suction blisters will be raised at the left volar forearm at the investigational Areas C or D (Figure 2). The allocation of the respective area for suction blister induction is decided via a randomization list.

After 4 additional weeks (Visit 5), 2 more suction blisters will be raised in each of the remaining so far non-blistered investigational Areas.

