5.1 Data collection methods

All data collectors will be trained in obtaining accurately the variables of interest. Paper source data (SD) will be used to document all study variables of interest (data collection forms see appendix 3).

Medical examination

The medical examination performed before inclusion will include a subject's interview on her medical history and a clinical examination, to make sure of the subject's eligibility.

Suction blister creation

The Suction blister model is an artificial and controlled technique for dermal-epidermal separation. Over the course of this study a total of 8 suction blisters with 8 mm in diameter are produced at the middle of the volar forearms of one volunteer. The comparisons of the blistering times (in minutes) will be used as outcome to detect possible treatment effects. Two suction blisters will be induced on each investigational area for two independent measurements of the blistering time. The technical procedure of suction blister wound creation is presented in the SOP Appendix 4.

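### Section 4.3 leaves every outcome without masked reading, although epidermal thickness could be read from coded OCT images; blistering time needs simple safeguards or a stated limitation

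*Combined protocol and SAP*

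**What the plan says.** Section 4.3 is one sentence: "Due to the nature of the intervention, neither the investigators nor the participants will be blinded". It does not mention separate outcome assessors, OCT readers or the analyst, and no other section of the protocol text adds masked assessment.

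Blistering time is judged by eye. Section 3.4 defines two moments. One is "Duration from start of suction pressure to appearance of first vesicles in minutes"; the other is the time to a full blister. Section 3.4 also says: "Because this is an exploratory study, no distinction is be made between primary and secondary outcomes". By function, though, blistering time carries the trial. Section 5.1 states: "The comparisons of the blistering times (in minutes) will be used as outcome to detect possible treatment effects". Section 2.2 gives the expected direction: "The main aim of this study is to investigate in a suction blister model, whether the use of a basic skin care formulation increases" the adhesion of the dermo-epidermal junction.

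"Epidermal thickness" is also listed in section 3.4 and is measured by OCT. The protocol does not say who reads it or whether the reader knows the treated side. On staff, section 5.1 says: "All data collectors will be trained in obtaining accurately the variables of interest". It gives no number of collectors and does not say what they know of the allocation.

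**The concern.** The comparator in section 3.3 is a bare forearm on the same woman. She cannot be blinded, and neither can the person who instructs her. That reason does not carry over to someone who measures a layer thickness on an image, and it does not by itself show that the person timing a blister must know the treated side.

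An aware reader knows which arm is expected to do better. If that knowledge moves the reading, the shift enters the treated-minus-control difference directly. Randomising the side does not remove it, because it follows the treatment wherever the treatment is allocated. Using each woman as her own control does not remove it either, and the two blisters per area do not average it out if the same aware person times both. Concealed envelopes (sections 4.1 and 4.2) guard against selection, not against this. Checking data entry against source (section 5.2) cannot detect a reading that was biased when it was written down.

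At stake is how far a small difference between arms can be read as a treatment effect.

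**Working it through.** The plan gives no figure that depends on blinding, and section 3.6 makes no formal sample size calculation, so there is nothing to reproduce. The check is mainly of the text.

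**1. Does the reason in section 4.3 apply to each reading?**
- *Participant:* yes. She applies the product to one arm only (section 3.3).
- *OCT thickness:* no. Once an image is stored, it can be measured without knowing whose arm it shows. Section 9 lists an OCT procedure (Appendix 7) and a separate procedure for determining epidermal thickness (Appendix 8), which suggests that thickness is determined as its own step. This is an inference, because the appendices appear by title only. Whether images are stored is not stated.
- *Blistering time:* only in part. It is judged live, with the participant present. The product is meant to remain on the skin (section 3.3), and the area letters give the side: A and B are right, C and D left (section 3.4). A person who never learned the treated side could still be masked in principle, but no such person is documented.

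**2. What could a reading shift do? (illustration)**
- Inputs: n = 12 women, each with a treated and an untreated arm (sections 2.3 and 3.6). The documents give no SD, so the unit is the SD of the within-subject difference.
- Assumption: a systematic shift b in favour of the treated arm, and no true effect. The documents give no value for b.
- SE of the mean difference = 1/√12 = 0.289 SD.
- Chance that the mean difference favours petrolatum = Φ(b/SE), by normal approximation.

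| b (SD) | b/SE | Chance of favouring petrolatum |
|---|---|---|
| 0 | 0 | 50% |
| 0.10 | 0.35 | 63.5% |
| 0.25 | 0.87 | 80.7% |
| 0.50 | 1.73 | 95.8% |

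The table concerns the direction of a mean difference. Section 5.3 plans medians and interquartile ranges, so it shows only that a descriptive comparison is also exposed. It does not show that any of these shifts is likely.

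**3. How large is the OCT batch?**
Assume all four areas are read twice (section 3.4) at each OCT visit in Table 1 (Visits 1, 3 and 5). That is 12 × 4 × 2 × 3 = 288 readings. The outcome table in section 3.4 also lists Visit 6, which would give 12 × 4 × 2 × 4 = 384. Fewer follow if blistered areas are not measured.

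**The case against.** The strongest reply is that this is a small, single-centre, exploratory study. It declares itself unblinded, ranks no outcomes and applies no tests (sections 3.4, 4.3 and 5.3). The main aim rests on blistering time, which is the reading hardest to mask. The reading that is easy to mask, OCT thickness, does not answer the main aim. Inspection intervals and reading rules may already be set in Appendices 4, 7 and 8. All of this stands, and it keeps the severity low.

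Several stronger readings are tempting but not supported:
- A reader might infer that section 4.3 rules out all blinding. It names investigators and participants and is silent on separate assessors, image readers and the analyst.
- A reader might infer that existing staff could mask the live timing at no cost. Section 5.1 says only that collectors are trained. The two people described as uninvolved or independent are the data manager, who prepares the allocation, and a data-entry verifier; neither is described as an assessor. Preparing both forearms identically to hide the product would be a new step and could disturb the hydration readings taken at the same visits.
- A reader might infer that masking was considered and dropped because it needs another assessor. The documents give only the kind of intervention as the reason.

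The reply does not answer the OCT point. Coding images needs no further assessor and no procedure on the participant.

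**Conclusion.** The point holds in a limited form. No outcome has a masked reading, and the stated reason does not cover the measurement of thickness on OCT images. Coding those images is a better method than the unblinded reading that section 4.3 implies. For blistering time the risk of detection bias is real, but it can be only partly reduced.

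The severity is minor. The size of any bias cannot be derived from the documents, and the figures above rest on assumed shifts and cannot be turned into minutes. A reader might want to express the harm as the rate at which a 95% confidence interval wrongly excludes zero. The plan has no interval and no test, so such rates would not describe this trial. Nor do the documents support saying that the trial could never separate a real gain from a reading effect. That is so only for differences about as large as the unknown bias.

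The conclusion assumes that OCT images can be stored and measured later, and that the appendices do not already provide for masking.

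**What to change.** **OCT thickness.** Amend sections 4.3 and 3.4 so that images are stored under a random code, for example one assigned by the data manager. The usual reader then measures them in one batch. Subject, side, area and visit stay unlinked until all thickness values are entered.

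**Blistering time.** State who calls the endpoint. Keep the treated side off the timing form. Inspect both arms at the same intervals, unless Appendix 4 already says so. Where existing staffing allows, have a collector who did not open the arm envelope call the endpoint. Otherwise, report unmasked visual timing as a detection-bias limitation when the main aim is interpreted.

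**Cost.** Protocol wording, a file-coding step and OCT results that arrive later. Residual product may still show on some images, and coding the images does nothing for bias in blistering time.

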5.1 Data collection methods

All data collectors will be trained in obtaining accurately the variables of interest. Paper source data (SD) will be used to document all study variables of interest (data collection forms see appendix 3).

Medical examination

The medical examination performed before inclusion will include a subject's interview on her medical history and a clinical examination, to make sure of the subject's eligibility.

Suction blister creation

The Suction blister model is an artificial and controlled technique for dermal-epidermal separation. Over the course of this study a total of 8 suction blisters with 8 mm in diameter are produced at the middle of the volar forearms of one volunteer. The comparisons of the blistering times (in minutes) will be used as outcome to detect possible treatment effects. Two suction blisters will be induced on each investigational area for two independent measurements of the blistering time. The technical procedure of suction blister wound creation is presented in the SOP Appendix 4.

5.2 Data management

The data manager creates an SPSS file and data of the SD are entered (single data entry). After data are entered, a random subset will be verified by an independent person (SD verification) who was not involved in the data entry so far.

5.3 Statistical methods

Demographic and other characteristics will be described using mean and spread parameters or proportions. The skin measurement results including the time(s) to blistering will be described using medians and interquartile ranges per skin area and time and displayed in grouped bar graphs. No statistical tests will be applied.

6 Methods: Monitoring

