2.3 Trial design

Exploratory randomized controlled study with a split body design on two investigational areas of the anterior side of both forearms.

3 Methods: Participants, interventions, and outcomes

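### Section 5.3 groups results by an undefined skin area and names neither the randomised treatment nor the within-subject petrolatum-minus-untreated difference

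*Combined protocol and SAP*

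**What the plan says.** Section 2.3 describes an "Exploratory randomized controlled study with a split body design on two investigational areas of the anterior side of both forearms". Under 3.3, "After that one arm will be randomly selected" for petrolatum and the other arm serves as the untreated control. Under 3.4, "Both arms will be subdivided in two investigational areas": A and B on the right forearm, C and D on the left. Section 4.1 uses two separate simple lists, one for the treated arm (left or right) and one for the area pair blistered first (A with C, or B with D). Each subject's remaining areas are blistered at Visit 5.

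The aim in 2.2 is whether the product increases dermo-epidermal adhesion, and 5.1 adds: "The comparisons of the blistering times (in minutes) will be used as outcome to detect possible treatment effects". The only description of the analysis is in 5.3: "The skin measurement results including the time(s) to blistering will be described using medians and interquartile ranges per skin area and time". Grouped bar graphs are planned, without a named grouping factor, and no tests. Treatment, control and paired difference do not appear there.

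**The concern.** The grouping unit in 5.3, skin area, is not defined, and the two possible readings give different tables.

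The only areas that the protocol names are anatomical, and some of its usage points that way: the caption of Figure 1, and metrics in 3.4 such as "Means of duplicate measurements per skin area in arbitrary units". Because the treated arm is drawn afresh for each subject, any of A to D can be treated in some subjects and untreated in others. A table by A to D would therefore mix the two conditions and would not address the aim.

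The other reading is treated versus untreated area. The medians then show the contrast, but each arm is summarised on its own. How large the effect is within a subject, and how many subjects show it, is what a split-body design offers, and the plan does not report it.

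A smaller point concerns hydration, epidermal thickness and skin temperature. Areas blistered at Visit 3 are left untreated afterwards (3.4), and 5.3 does not say how any later measurements on them are kept apart from skin still under treatment. Blistering time at Visit 5 is not affected, because it uses only areas not yet blistered.

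**Working it through.** The plan has no figure of its own to reproduce: 3.6 gives 12 subjects without a calculation. The one checkable count is 2 arms × 2 areas × 2 blisters = 8, which agrees with 5.1.

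**Inputs from the documents:** 12 subjects (3.6); simple randomisation of arm and of area pair, taken as probability 0.5 each (4.1). **Assumptions, because the documents give no values:** normal data with unit SD per arm, an effect of 1 SD, between-arm correlation ρ from 0 to 0.9.

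**Reading 1: areas A to D, outcome measured on all areas in all 12 subjects.** Let k be the number treated on the right, k ~ Bin(12, 0.5). Right minus left would carry (k − (12 − k))/12 = (2k − 12)/12 of the mean effect.
- Exactly zero (k = 6): 924/4096 = 0.226.
- At most one third in size (k = 4 to 8): 3498/4096 = 0.854.
- Opposite sign (k ≤ 5): 1586/4096 = 0.387.

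**Reading 1: blistering time, A versus C at one visit.** The number of contributing subjects is m ~ Bin(12, 0.5), about 6, and k given m is Bin(m, 0.5). The share is (2k − m)/m: zero with probability 0.161, opposite sign 0.419. Medians behave much like means. With m = 6 and ρ = 0.7, the average difference of medians is 0.00, 0.37, 0.70 and 1.00 SD for k = 3, 4, 5 and 6, against (2k − 6)/6 = 0.00, 0.33, 0.67 and 1.00.

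**Reading 2: treated versus untreated area, n = 12** (200,000 simulated trials, in SD units). The variance ratio is (SD of the difference of the two medians ÷ SD of the median paired difference)².

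| ρ | SD, difference of medians | SD, median paired difference | Variance ratio | Mean IQR of paired difference |
|---|---|---|---|---|
| 0 | 0.485 | 0.483 | 1.0 | 1.70 |
| 0.3 | 0.430 | 0.405 | 1.1 | 1.42 |
| 0.5 | 0.384 | 0.343 | 1.3 | 1.20 |
| 0.7 | 0.326 | 0.265 | 1.5 | 0.93 |
| 0.9 | 0.224 | 0.153 | 2.1 | 0.54 |

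The marginal IQR per arm averages 1.20 SD, and the last column follows it as 1.20 × √(2(1 − ρ)). The paired IQR is therefore wider than the marginal IQR below ρ = 0.5 and narrower above it.

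**Optional interval for the median difference.** With 12 complete pairs, the 3rd to 10th ordered differences cover with probability 1 − 2 × P(Bin(12, 0.5) ≤ 2) = 1 − 2 × (1 + 12 + 66)/4096 = 0.961.

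**Post-blister visits.** At Visits 4 and 5 each arm still has one area not blistered at Visit 3. Both lie at the same position, because the list pairs A with C and B with D. By Visit 6 every area has been blistered and Table 1 shows the product returned at Visit 5, so no unblistered, still-treated skin remains. Section 3.4 lists hydration and thickness at Visit 6; Table 1 marks them only to Visit 5.

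**The case against.** The strongest reply is that the rest of the protocol makes the intention plain: a randomised controlled design, an untreated control arm, an adhesion objective and blistering times compared for treatment effects. Read with these, skin area may simply mean treated or control area. Usage in the protocol is also mixed: the lettered sites are called investigational areas, the eligibility criteria use skin area generically, and 5.3 uses no letters. This stands, and the anatomical reading cannot be treated as established.

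A reader might infer that the plan will lose or reverse the treatment effect. The documents do not support that. Section 5.3 plans summaries, and no section plans a right-minus-left or A-minus-C contrast; the shares above describe what such a comparison would show if someone made it. Nor should the wrong-sign rate of A minus C (about 0.50) be set against the rate when summarised by treatment (0.020 or less at an assumed 1 SD). The first rests on about 6 subjects and the second on 12; with 6 subjects the by-treatment rate is up to 0.064.

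It is also fair to say that pairing gains no precision at zero correlation and little at 0.3, that the study is exploratory, and that the documents do not say outright whether healing areas are measured at later visits. None of this supplies the missing contrast. A descriptive plan can still say which difference it will describe. With no outcome hierarchy (3.4) and no blinding (4.3), it is better said before the data are seen.

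**Conclusion.** The point holds as an omission in 5.3 that should be corrected; it does not invalidate the study. The plan names neither the randomised treatment nor a within-subject contrast, and its grouping unit is undefined.

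On the anatomical reading, the summaries pool treated and untreated skin. The binomial figures for that reading rest only on 12 subjects and simple randomisation with equal probability. On the treatment reading, the contrast is visible but its within-subject consistency is not. The precision gain of 1.0 to 2.1 in variance rests entirely on assumed correlations and normal data. On either reading, the contrast can be recovered from the allocation and the separately recorded values. The absence of tests is an acceptable choice for an exploratory study and is not part of the criticism.

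**What to change.** Rewrite the outcome paragraph of 5.3 as follows.

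- Summarise by randomised treatment (petrolatum, untreated) and visit.
- Treat the two blistering times separately: one is "Duration from start of suction pressure to appearance of first vesicles in minutes", the other runs to the full blister. For each, take one value per subject, arm and visit, for example the mean of the two blisters unless Appendix 4 sets a rule.
- Report the median and IQR of the within-subject petrolatum-minus-untreated difference at Visits 3 and 5, with paired individual plots. Optionally add the interval from the 3rd to the 10th ordered difference (96.1% coverage with 12 pairs).
- Report the same paired difference for hydration and epidermal thickness at their visits, and for skin temperature at Visits 3 and 5.
- For these non-blister outcomes at Visits 4 and 5, base the contrast on the areas not blistered at Visit 3, measured at Visit 5 before blister induction. Show any measurements on previously blistered areas separately.
- Present any Visit 6 measurements descriptively only, without a treatment contrast. Section 3.4 and Table 1 disagree on whether hydration and thickness are measured at Visit 6, and must be reconciled.

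The cost is one paragraph and revised table layouts. Subjects, visits and data stay the same, no hypothesis test is added, and the study remains exploratory.

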After the blister has been raised, the blister fluid will be punctured and a dressing applied to allow the wound to heal. The skin areas where suction blisters have been raised after 4 weeks will not be treated during the following 8 weeks.

Before any measurements or induction of the suction blisters, the study volunteers will be requested to acclimatize for 30 minutes at 40 to 60 % relative humidity and a temperature of 20 to 22 °C with having both forearms uncovered.

Sequence of measurements (Visit 1, 2, 3, 4, 5 and 6)

- (1) Skin surface temperature
- (2) Stratum corneum hydration (SCH)
- (3) Epidermal and dermal hydration
- (4) Skin thickness

Measurements will be performed two times per measurement area. Every value will be recorded separately.

Figure 1. Localization of investigational skin areas

[figure not shown]
[figure not shown]

Figure 2. Localization of suction blisters

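### Hydration and epidermal thickness are measured at Visit 1, before the treated forearm is drawn, but section 5.3 plans no within-woman treatment difference adjusted for them

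*Combined protocol and SAP*

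**What the plan says.** - **Order of events.** Section 3.3 states that "baseline skin measurements will be conducted (Table 3). After that one arm will be randomly selected". The Visit 1 readings therefore precede the allocation and cannot have been influenced by it.
- **What is read at Visit 1.** Section 3.4 lists both hydration measures at "Visit 1, Visit 2, Visit 3, Visit 4, Visit 5, Visit 6" and epidermal thickness at "Visit 1, Visit 3, Visit 5, Visit 6". Table 1 in section 3.5 has no tick for these at Visit 6, but both sources include Visit 1.
- **Coverage.** "Measurements will be performed two times per measurement area" (section 3.4), so each of areas A to D has its own Visit 1 value.
- **Analysis.** Section 5.3 is the whole plan: "The skin measurement results including the time(s) to blistering will be described using medians and interquartile ranges per skin area and time", shown as grouped bars, and no tests are applied. It names no change from Visit 1, no baseline-adjusted value and no within-woman difference between forearms.
- **Blistering time.** Section 5.1 says "The comparisons of the blistering times (in minutes) will be used as outcome to detect possible treatment effects". It is recorded only at Visits 3 and 5.

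**The concern.** A pre-randomisation reading of the same variable on the same skin can correct a later comparison for a difference that was there from the start. This plan collects such a reading for three of its five listed skin outcomes and then only displays it.

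Display does not do the work of adjustment. Medians and interquartile ranges by area and visit do not show how a woman's Visit 1 forearm difference relates to her later one, and a difference of group medians is not a median of within-woman differences. A reader of the report could not recover the adjusted contrast from the planned tables or graphs.

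At stake is precision in a study of 12 women. A chance difference between the forearms at Visit 1 can look in part like a petrolatum effect, or can partly hide one. The study is also unblinded (section 4.3). If the plan is silent, the choice between raw, change and adjusted values is made after the data are seen.

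**Working it through.** **Inputs.** n = 12 (section 3.6, stated without a formal calculation, so there is no planned figure to reproduce). The treated side is drawn by simple randomisation (section 4.1). Rho, the correlation between a woman's Visit 1 and later petrolatum-minus-untreated differences, is not in the documents; a range is assumed. Everything is in units of the SD of the within-woman forearm difference, whose absolute size is also not given.

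**1. Chance imbalance at Visit 1.** The mean of 12 forearm differences has standard error 1/sqrt(12) = 0.289 SD, with a 95% range of ±1.96 × 0.289 = ±0.57 SD. Under normality the imbalance exceeds 0.3 SD in either direction with probability 30%, and 0.5 SD with probability 8%.

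**2. How much carries forward.** With equal SDs at the two visits, the expected carry-over is rho times the Visit 1 imbalance. An imbalance of 0.3 SD leaves 0.3 × 0.3 = 0.09 SD at rho 0.3 and 0.3 × 0.9 = 0.27 SD at rho 0.9.

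**3. Variance of the mean treatment difference, relative to the unadjusted later difference (1.00).**
- Regression on the Visit 1 difference, evaluated at a Visit 1 difference of zero: (1 − rho²)(1 + 1/(n − 3)) = (1 − rho²) × 10/9. The factor 10/9 is the price of estimating the slope from 12 women.
- Simple change from Visit 1: 2(1 − rho), assuming equal variances at the two visits.

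| rho | Regression-adjusted | Change from Visit 1 |
|---|---|---|
| 0 | 1.11 | 2.00 |
| 0.3 | 0.91 × 1.111 = 1.01 | 1.40 |
| 0.5 | 0.75 × 1.111 = 0.83 | 1.00 |
| 0.7 | 0.51 × 1.111 = 0.57 | 0.60 |
| 0.8 | 0.36 × 1.111 = 0.40 | 0.40 |

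A simulation at n = 12 gave standard errors for the adjusted estimate of 0.290, 0.264 and 0.217 at rho 0.3, 0.5 and 0.7, against 0.289 unadjusted. Squared ratios are 1.01, 0.84 and 0.56, in agreement with the formula.

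**4. Break-even.** Regression: (1 − rho²) × 10/9 = 1 gives rho² = 0.1, so rho is about 0.32. Simple change: 2(1 − rho) = 1 gives rho = 0.5.

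**5. Equivalent sample size where it helps.** 12/0.83 is about 14 women at rho 0.5, 12/0.57 about 21 at 0.7, and 12/0.40 = 30 at 0.8.

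**The case against.** The case for leaving the plan alone has several parts.

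- **There is no contrast to adjust.** Section 5.3 summarises by area. The areas are tied to the right or left arm, while the treated arm varies from woman to woman, so the per-area medians mix treated and untreated skin. The first gap is the missing petrolatum-minus-untreated difference. This stands: adjustment presupposes that difference. It is still a further step, because a correctly paired later difference would ignore Visit 1 just the same.
- **The gain is unknown and may be nil.** Rho here is a correlation of forearm differences. Differencing within a woman already removes stable variation between women, so rho may be well below the correlation of the raw readings. This stands, and it is why the range above includes values at which adjustment loses slightly.
- **The study is exploratory and descriptive by choice.** Regression on 12 points adds a mean-based estimate to a plan built on medians, and the variance figures above concern means. That stands as a reason to keep the planned medians and place the adjusted value beside them. It is not a reason to omit it: adjustment is estimation and needs no test.
- **The main question lies elsewhere.** The aim in section 2.2 is dermo-epidermal adhesion, and section 5.1 names blistering time as the outcome for treatment effects. This stands. Section 3.4 nevertheless declines to rank the outcomes, so the three affected ones count on the protocol's own terms.
- **Visit 1 is shown.** True, but by area, which reveals neither the treated-versus-untreated imbalance nor the within-woman association.

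**Conclusion.** The omission is real and worth correcting, with modest consequences. Pre-randomisation values of both hydration measures and epidermal thickness are collected in every area, and section 5.3 does not use them to adjust any treatment contrast. The chance Visit 1 imbalance has a standard error of 0.29 SD of the forearm difference. Adjustment changes the variance of the mean difference by a factor between 1.11 (rho 0) and 0.40 (rho 0.8), and helps only if rho exceeds about 0.32.

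Three stronger readings might be inferred, and the documents support none of them.

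- *The planned comparison is biased.* The treated side is drawn at random, so the unadjusted contrast is unbiased on average. The issue is chance imbalance and lost precision.
- *A Visit 1 difference stays in full in every later value, and adjusting is certain to raise precision.* Only a fraction rho carries forward on average, and nothing in the documents puts rho above the break-even.
- *The blistering results are compromised.* Blistering time has no Visit 1 value and is not affected.

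Skin surface temperature is left out of this point: the outcome table gives it only at Visits 3 and 5, although the measurement sequence in the same section names it for all six visits.

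The figures assume 12 women with complete data, roughly normal differences and a linear relation between Visit 1 and later differences. The change-score column also needs equal variances at the two visits.

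**What to change.** Add to section 5.3, for stratum corneum hydration, epidermal and dermal hydration, and epidermal thickness:

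1. At each visit, form each woman's petrolatum-minus-untreated difference over matched areas (A with C, B with D), using only areas not yet blistered, and take the Visit 1 difference from the same areas. One matched pair remains after Visit 3 and none after the Visit 5 blisters, so this covers the later visits up to Visit 5.
2. Report the later difference unadjusted, as median and interquartile range in keeping with the current plan.
3. Beside it, report the difference adjusted for the Visit 1 difference, by linear regression of the later on the Visit 1 difference, evaluated at a Visit 1 difference of zero. Present it descriptively, with no test.

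Regression is preferable to simple change from Visit 1, which is worse than no adjustment when rho is below 0.5.

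The cost is a few lines of text and minor programming, with no new measurements or visits. Statistically it costs one degree of freedom, and at most about 11% more variance if Visit 1 turns out not to predict later values. Showing both values lets the reader see whether the adjustment matters.
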